5.3. Lifestyle Considerations

5.3.1. Meals and Dietary Restrictions

In both Treatment Periods, participants will be required to take their oral dose of GSK3640254 with a moderate fat meal (approximately 600 calories with approximately 30% of calories from fat). The meal will be given 30 minutes before dosing and must be consumed within 25 minutes.

In Treatment Period 1, participants will be required to fast from insertion of the bile string until the completion of the IV infusion, a period of approximately 4 hours. In Treatment Period 2, participants will also be required to fast from insertion of the bile string until 5.5 hours post dose.

In both treatment periods at the times defined in the [SoA](#) a standard, small high-fat meal will be provided. Meal times are specified in both treatment periods for Day 1, on all other days, meals will be served at the standard times of the clinical site.

Participants will refrain from consumption of Seville oranges, grapefruit or grapefruit juice, pomelos, exotic citrus fruits, grapefruit hybrids, or their fruit juices from 7 days before the start of study intervention until the follow-up visit.

During the inpatient stays, participants will refrain from consumption of nuts and seeds, or other foods that may cause issues with homogenization of feces. Peas must not be consumed from Day -1 until 48 hours after each oral dose in both treatment periods (to avoid potential complications with retrieval of the steel ball from the bile string device prior to sample homogenization).

No water is allowed until 2 h after oral dosing (apart from rinsing the oral suspension dose of [¹⁴C]-GSK3640254); water is allowed *ad libitum* at all other times.

Adequate hydration should be encouraged to help facilitate stool sample production. If needed, participants may consume prunes or prune juice to facilitate stool samples.

5.3.2. Caffeine, Alcohol, and Tobacco

Participants will abstain from alcohol for 24 h before the screening visit until the follow-up visit.

Participants must not be current smokers (no smoking for at least 6 months before the screening visit). Use of tobacco- or nicotine-containing products (including nicotine patches and other delivery devices such as vaporizers) will not be allowed from screening until after the final follow-up visit.

5.3.3. Activity

Participants will abstain from strenuous exercise for 24 hours before each blood collection for clinical laboratory tests. Participants may participate in light recreational activities during studies (e.g., watching television, reading).

5.4. Screen Failures

Screen failures are defined as participants who consent to participate in the clinical study but are not subsequently enrolled in the study. A minimal set of screen failure information is required to ensure transparent reporting of screen failure participants to meet the Consolidated Standards of Reporting Trials (CONSORT) publishing requirements and to respond to queries from regulatory authorities. Minimal information includes demography, screen failure details, eligibility criteria, and any SAEs.

Individuals who do not meet the criteria for participation in this study (screen failure) may not be rescreened.

6. STUDY INTERVENTION

Study intervention is defined as any investigational intervention(s), marketed product(s), placebo, or medical device(s) intended to be administered to a study participant according to the study protocol (see [Table 4](#)).

6.1. Study Intervention(s) Administered

Detailed instructions for dosing will be provided in the SRM.

Table 4 Treatments administered during the study

Study Intervention Name:	[¹⁴ C]-GSK3640254 IV Solution-for-Infusion	[¹⁴ C]-GSK3640254 Oral Powder-in-Bottle	GSK3640254 Oral Tablet
Dosage formulation:	IV solution	Powder-in-bottle	Oral tablet
Treatment Period	1	2	1
Unit dose strengths:	Strength: 10 µg/mL Dosage Level: 100 µg	Strength: 85 mg Dosage Level: 85 mg	Strength: 2 x 100 mg tablet Dosage Level: 200 mg
Route of Administration:	IV infusion	Oral	Oral
Dosing instructions:	Administer 10 mL intravenously over 1 h.	Administer total 85 mg dose (reconstituted into a suspension using 25 mL vehicle just before dosing) with meal in the morning.	Two tablets taken with meal in the morning with 240 mL of room temperature water
Manufacturer:	Drug product: Hammersmith Medicines Research (HMR)	Drug product: HMR	GSK Ware, UK
Physical Description:	A clear, colourless solution free from visible particulates	White powder (white to slightly coloured for the reconstituted suspension)	White, round shaped, film coated tablets containing no markings

6.2. Preparation/Handling/Storage/Accountability

The investigator or designee must confirm appropriate temperature conditions have been maintained during transit for all study intervention received and any discrepancies are reported and resolved before use of the study intervention.

Only participants enrolled in the study may receive study intervention and only authorized site staff may supply or administer study intervention. All study interventions must be stored in a secure, environmentally controlled, and monitored (manual or automated) area in accordance with the labeled storage conditions with access limited to the investigator and authorized site staff.

The investigator, institution, or the head of the medical institution (where applicable) is responsible for study intervention accountability, reconciliation, and record maintenance (i.e., receipt, reconciliation, and final disposition records).

A description of the methods and materials required for preparation of [¹⁴C]-GSK3640254 solutions for IV infusion and oral administration is provided in the Technical Agreement (TA). A Quality Agreement will be in place with the contract research organization (CRO) performing the manufacturing operations.

Further guidance and information for the final disposition of unused study intervention are provided in the TA.

Under normal conditions of handling and administration, study intervention is not expected to pose significant safety risks to site staff. Take adequate precautions to avoid direct eye or skin contact and the generation of aerosols or mists. In the case of unintentional occupational exposure notify the monitor, Medical Monitor and/or GSK study contact.

A Material Safety Data Sheet (MSDS)/equivalent document describing occupational hazards and recommended handling precautions either will be provided to the investigator, where this is required by local laws, or is available upon request from GSK.

Dose administrators must follow site-specific procedures for handling radiolabelled GSK3640254.

6.3. Measures to Minimize Bias: Randomization and Blinding

- This is an open-label study with no randomization and no blinding of participants, site personnel, or sponsor personnel.
- Eligibility will be established during the Screening Period. A cohort of six participants will be admitted to the clinical research unit on the same day and will complete Period 1 and Period 2 on the same schedule with the same study interventions. This approach minimizes potential bias associated with temporal effects.

6.4. Study Intervention Compliance

Individual doses will be prepared for each participant from a bulk supply and will be confirmed by a second member of the study site staff.

All participants will receive their doses directly from the investigator or designee, under medical supervision. The date and time of each dose administered in the clinic will be recorded in the source documents and reported in the case report form (CRF). The dose of study intervention and study participant identification will be confirmed at the time of dosing by a member of the study site staff other than the person administering the study intervention. For oral doses, study site personnel will examine each participant's mouth to ensure that the study intervention was ingested. For IV doses, administration will be documented in the source documents and reported in the CRF.

6.5. Concomitant Therapy

Any medication or vaccine (including over-the-counter or prescription medicines, vitamins, and/or herbal supplements) that the participant is receiving at the time of enrollment must be discontinued by 15 days before the start of the study intervention. These must be recorded along with:

- reason for use
- dates of administration, including start and end dates
- dosage information, including dose and frequency

The Medical Monitor should be contacted if there are any questions regarding concomitant or prior therapy.

Participants must abstain from taking prescription and non-prescription drugs (including vitamins and dietary and herbal supplements) within 14 days before the start of study intervention until completion of the follow-up visit unless approved by the Investigator in conjunction with a VH/GSK Medical monitor.

Special warnings and precautions for use of GSK3640254 are given in the IB, Section 6.

6.6. Dose Modification

No dose modification is allowed.

6.7. Intervention after the End of the Study

Participants will not receive any additional study intervention from GSK after completion of the study because only healthy participants are eligible for study participation.

7. DISCONTINUATION OF STUDY INTERVENTION AND PARTICIPANT DISCONTINUATION/WITHDRAWAL

[figure not shown]
7.1. Discontinuation of Study Intervention

7.1.1. Liver Chemistry Stopping Criteria

Liver chemistry stopping and increased monitoring criteria have been designed to assure participant safety and evaluate liver event etiology.

Study intervention will be discontinued and be discontinued from the study for a participant if liver chemistry stopping criteria are met:

Figure 2 Phase I Liver Chemistry Stopping Criteria – Liver Stopping Event Algorithm

Liver Safety Required Actions and Follow up Assessments Section can be found in [Appendix 7: Liver Safety: Required Actions and Follow-up Assessments](#).

Study intervention restart or rechallenge after liver chemistry stopping criteria are met by any participant in this study is not allowed.

7.1.2. QTc Stopping Criteria

The same correction formula (QTcF) must be used for each individual participant to determine eligibility for and discontinuation from the study. This formula may not be changed or substituted once the participant has been enrolled.

- The ECG taken on Day –1 of each treatment period will be a single reading to confirm eligibility. In each study period, the Day 1 pre-dose timepoint will have triplicate averaged QTcF (over a brief approximately 5 to 10 minute recording

period). This pre-dose triplicate averaged QTcF value will serve as the baseline for each applicable study period.

- An enrolled participant that develops an on-treatment QTcF >500 ms or an increase from Baseline QTcF >60 ms should have two repeat unscheduled ECGs within 10 minutes. Using these triplicate ECGs, if the average QTcF >500 ms or an increase from Baseline QTcF >60 ms, the participant will be withdrawn from the study. Finally, this participant should have repeated unscheduled ECGs until their QTcF measurement returns to their original averaged QTcF value at Day 1 pre-dose.

See the [SoA](#) for data to be collected at the time of treatment discontinuation and follow-up and for any further evaluations that need to be completed.

7.1.3. Individual Participant Laboratory Abnormality and AE Stopping Criteria

A participant must permanently discontinue study intervention and be discontinued from the study for the pre-specified reasons below. Please refer to Section [8.2.5](#) and Section [8.2.6](#) for details on suicidal risk and GI toxicity monitoring, respectively.

- Severe pain, redness, bleeding or swelling at the infusion site.
- Liver chemistry abnormalities exceeding the threshold criteria (see Section [7.1.1](#)).
- QTc result meeting the stopping criteria (see Section [7.1.2](#))
- SAE considered related to study intervention
- Any clinically significant AE deemed to require discontinuation of study intervention
- Any Grade 3 or higher rash or Grade 2 rash with evidence of systemic involvement
- Any allergic or hypersensitivity reactions to either formulation
- Any Grade 3 or higher psychiatric AE
- New onset suicidal ideation
- Any Grade 3 or higher AE related to study intervention
- Any Grade 4 AE or laboratory abnormalities (with the exception of an asymptomatic Grade 4 cholesterol, CPK, or triglyceride)

7.1.4. Columbia-Suicide Severity Rating Scale Criteria

Emergence of any positive (abnormal) response confirmed by the investigator on a clinician (or qualified designee) administered C-SSRS during the treatment phase of the study, the participant will undergo immediate clinical assessment of suicidality (by the investigator or a consulting psychiatrist). Emergence of new onset suicidal ideation or a

Grade 3 or higher psychiatric AE will result in immediate discontinuation and urgent specialist psychiatric evaluation and management.

Refer to the [SoA](#) for data to be collected at the time of intervention discontinuation and follow-up and for any further evaluations that need to be completed. See Section [8.2.5](#) for more details.

7.1.5. COVID-19

A participant must permanently discontinue study intervention and be discontinued from the study if they have COVID infection as clinically determined by the investigator (suspect, probable, or confirmed using the most recent version of the WHO case definition) or by laboratory testing.

7.1.6. Other study stopping criteria

The study will be halted if there is a SAE or 2 severe AEs, considered to be related to the investigational medicinal product (IMP). If following an internal safety review, it is appropriate to restart the trial, a substantial amendment will be submitted to the Medicines and Healthcare Regulatory Authority (MHRA) and Research Ethics Committee (REC). The trial will not restart until the amendment has been approved by the MHRA and REC.

7.2. Participant Discontinuation/Withdrawal from the Study

A participant may withdraw from the study at any time at his own request or may be withdrawn at any time at the discretion of the investigator for safety, behavioural, compliance or administrative reasons. If study intervention is permanently discontinued, the participant will remain in the study for confirmation of excretion of radioactivity (see Section [4.1.3](#)). Participants who withdraw from the study early should undergo an early withdrawal visit as defined in the SoA.

If the participant withdraws consent for disclosure of future information, the sponsor may retain and continue to use any data collected before such a withdrawal of consent.

If a participant withdraws from the study, he may request destruction of any samples taken and not tested, and the investigator must document this in the site study records.

The investigator will record in the source documents the results of follow-up examination of withdrawn participants, if the participant gives their consent.

In the event of vomiting directly after oral dosing withdrawal may be considered. Refer to Section [8.5.4](#) for details.

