1.3. Schedule of Activities (SoA)

The timing and number of planned study assessments, including safety and pharmacokinetic assessments, may be altered during the study based on newly available data (e.g., to obtain data closer to the time of peak plasma concentrations) to ensure appropriate monitoring. Participants who withdraw from the study early should be subject to those assessments that would be required at discharge in that treatment period, if participants agree.

Participants who are withdrawn and discharged from the study due to COVID-19 infection will return to the site for follow up assessments after 2 weeks.

Any changes in the timing or addition of time points for any planned study assessments must be documented and approved by the relevant study team member and then archived in the sponsor and site study files but will not constitute a protocol amendment. The Institutional Review Board (IRB)/Independent Ethics Committee (IEC) will be informed of any safety issues that require alteration of the safety monitoring scheme or amendment of the Informed Consent (ICF).

If assessments are scheduled for the same nominal time, the assessments should occur in the following order:

1. vital signs
2. 12-lead electrocardiogram (ECG)
3. blood draws
4. other assessments

Note: The timing of the assessments should allow the blood draw to occur at the exact nominal time.

Table 1 SoA Screening, Follow up and Early Withdrawal

Procedure	Screening¹ (Up to 30 days before first dose)	Follow up/Early Withdrawal (7 – 14 days after the last assessment)	Comments
Informed consent	X		
Medical history (including drug/alcohol use)	X		
Demography	X		
12-lead ECG	X	X	Single ECG measurements will be obtained at screening. Repeats can be obtained if the original reading cannot be interpreted. See Section 8.2.
Vital signs	X	X	Single measurements will be obtained for all parameters. Repeats can be obtained if the original reading cannot be interpreted. See Section 8.2.
Drugs of abuse screen	X		
Alcohol, cotinine, & CO breath tests	X		
HIV and hepatitis B and C screen	X		
Laboratory safety tests (incl. LFTs)	X	X	
Physical exam	X-full	X-brief	Details of full and brief physical exams in Section 8.2.1
Columbia-Suicide Severity Rating Scale (C-SSRS)	X	X	Details included in Section 8.2.5
Blood samples for total background radioactivity	X		

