8.5.4. Vomitus collection (if occurs)

Any episodes of vomiting should be recorded in the CRF as an adverse event.

If a participant vomits within the first 4 h after oral dosing, the participant will be considered unsuitable for evaluation and will be withdrawn from the study. Even if withdrawn, participants should remain in the clinic and samples collected until the discharge criteria outlined in Section [4.1.3](#) are met. Should the participant vomit after the first 4 h post oral dosing, the participant will not be withdrawn.

If a participant vomits any time during or after IV dosing, the participant will not be withdrawn.

As practical, the vomitus will be collected and the amount of radioactivity present in the vomitus estimated, using the sample handling procedure described for quantifying radioactivity in stools. During dosing, staff should ensure that each participant has a suitable pre-weighed plastic collection vessel available for that purpose.

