1.2.2. Estimands**Table 3 Estimands**

Objective	Estimand Category	Estimand			Population Level Summary Measure
		Variable/Endpoint	Analysis Set	Intercurrent Event Strategy	
Primary Objective: To determine parent GSK3640254 and total drug-related radioactivity systemic concentrations following a single IV microtracer dose of [¹⁴ C]-GSK3640254 (with an oral dose of non-radiolabelled GSK3640254) and oral dose of [¹⁴ C]-GSK36402541	Primary 1	AUC(0-inf), AUC(0-t), Cmax, tmax and t1/2 of parent and total drug-related material (radioactivity) in plasma	PK	Subject withdrawal or AE occurrence (treatment policy)	No adjustments will be made for the occurrence of any intercurrent events. Estimation will be done based upon observed data.
	Supplementary 1	Volume of distribution at steady-state (Vss) and clearance (CL) of parent after IV dose (Period 1 only)	PK	See Primary 1	
	Supplementary 2	Renal clearance of	PK	See Primary 1	

CONFIDENTIAL

Statistical Analysis Plan 213051

Objective	Estimand Category	Estimand			Population Level Summary Measure
		Variable/Endpoint	Analysis Set	Intercurrent Event Strategy	
		parent (CLr) after IV and oral administration			
	Supplementary 3	Oral clearance (CL/F) and apparent volume of distribution (Vz/F) for the parent following oral administration	PK	See Primary 1	
To calculate the absolute oral bioavailability of GSK3640254	primary 2	Direct estimation of absolute oral bioavailability (F), indirect calculation of fraction of drug escaping first pass hepatic clearance (Fh),	PK	See Primary 1	

CONFIDENTIAL

Statistical Analysis Plan 213051

Objective	Estimand Category	Estimand			Population Level Summary Measure
		Variable/Endpoint	Analysis Set	Intercurrent Event Strategy	
		fraction absorbed (Fa) and fraction of drug escaping gut metabolism (Fg).			
To determine the rate and extent of excretion of total radioactivity in urine and feces and the total recovery of radioactivity, following IV and oral administrations of [¹⁴ C]-GSK3640254	Primary 3	Urinary and fecal cumulative excretion as a percentage of the total radioactive dose		See Primary 1	
Key Secondary objective : To determine the blood:plasma ratio of [¹⁴ C]-GSK3640254-related materials (total radioactivity)	Secondary	Blood:plasma ratio of [¹⁴ C]-GSK3640254-related materials (total radioactivity).	PK	See Primary 1	

CONFIDENTIAL

Statistical Analysis Plan 213051

Objective	Estimand Category	Estimand			Population Level Summary Measure

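### The stopping rules take a participant out of the study while Protocol 7.2 keeps him in for radioactivity recovery, and the SAP does not say how an excreta collection that ends early is handled

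*Protocol*

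**What the plan says.** **Out of the study.** Protocol 7.1.1 (liver chemistry): "Study intervention will be discontinued and be discontinued from the study for a participant if liver chemistry stopping criteria are met". Protocol 7.1.2 (QTc), once the averaged repeat ECGs confirm the finding: "the participant will be withdrawn from the study". Protocol 7.1.3 (laboratory abnormalities and adverse events): "A participant must permanently discontinue study intervention and be discontinued from the study for the pre-specified reasons below". Protocol 7.1.5: "A participant must permanently discontinue study intervention and be discontinued from the study if they have COVID infection". The text in 1.3 goes further for that last group: "Participants who are withdrawn and discharged from the study due to COVID-19 infection will return to the site for follow up assessments", with the return set at two weeks.

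**Remains in the study.** Protocol 7.2: "If study intervention is permanently discontinued, the participant will remain in the study for confirmation of excretion of radioactivity". It refers to 4.1.3 for how this is done, and the title of 4.1.3 limits that section to Period 2.

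**Both at once.** Protocol 8.5.4, for a participant withdrawn because he vomited within 4 h of oral dosing: "Even if withdrawn, participants should remain in the clinic and samples collected until the discharge criteria outlined in Section" 4.1.3 are met. No stopping rule in 7.1 has an equivalent sentence.

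**The SAP.** Table 3 applies a treatment-policy strategy to withdrawal and adverse events: "No adjustments will be made for the occurrence of any intercurrent events". Estimation is from observed data. Cumulative urinary and faecal excretion is listed as a primary endpoint (5.2.1). Table 5 builds it by adding up collection intervals, and 5.2.2 has it summarised and listed.

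**The concern.** Mass balance depends on complete collection: a participant's cumulative recovery means what it should only if his urine and faeces were collected until excretion was essentially finished. In 7.1.3 and 7.1.5 the stopping event orders permanent discontinuation of study intervention, which is the condition that 7.2 attaches to staying in the study. One event therefore triggers two instructions that point in different directions. A site following 7.1 literally could let the participant go, and a site following 7.2 would keep collecting.

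Two things would be at stake. A primary endpoint measured in about six men could contain a partial total, and elimination of the radioactive dose in that participant would go unconfirmed. Treatment policy does not help, because it relies on data gathered after the intercurrent event, and those are the data that 7.1 may stop.

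**Working it through.** **Step 1. The sections side by side.**

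| Protocol section | Trigger | Participant's status | Does excreta collection continue? |
|---|---|---|---|
| 7.1.1 | Liver chemistry | Out of the study | Not stated |
| 7.1.2 | QTc | Withdrawn | Not stated (only repeat ECGs) |
| 7.1.3 | Laboratory/AE list | Out of the study | Not stated |
| 7.1.5 with 1.3 | COVID-19 | Out, discharged, back after 2 weeks | Not stated; discharge ends collection in the unit |
| 7.2 | Permanent discontinuation of intervention | Remains | Yes, by reference to 4.1.3 (Period 2) |
| 8.5.4 | Vomiting within 4 h of oral dose | Withdrawn | Yes, to the 4.1.3 criteria |

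Section 7.1.4 speaks only of immediate discontinuation, but the same psychiatric events are listed in 7.1.3.

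**Step 2. What a stopping rule can still change.** Each period has one dosing day (4.1.1, 4.1.2). After the Period 2 dose no study intervention is left to stop. Apart from safety follow-up, the main thing the rule still decides is whether the participant stays, and on that point 7.1 and 7.2 differ. After a Period 1 event, 7.2 gives no recovery criterion at all, because 4.1.3 does not cover Period 1. The only available benchmark there is the planned 0–168 h collection in 8.5.2 and 8.5.3.

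**Step 3. Following a truncated collection through the SAP.**
- Analysis set (section 4): anyone in the safety set with a single PK result qualifies; nothing concerns complete excreta.
- Strategy (Table 3): treatment policy, observed data, no adjustment.
- Derivation (Table 5): cumulative amounts and percentages are sums over intervals.
- Zero rule (5.2.1.2.2): NQ and NS values become zero. NS is defined for a participant who did not void in the interval, not for one who has left.
- Intervals after departure: not addressed. Section 5.2.1.1 refers PK data-handling conventions to the Output and Programming Specification (OPS).

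If those intervals are coded NS, or if the total is simply the sum of what was collected, the partial total enters the mean. If the later cumulative intervals are left missing, the participant drops out of the later means. The SAP does not choose between these.

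**Step 4. Size.** The plan states no expected recovery, so there is no figure to reproduce, and what follows is illustration. Inputs: n = 6 (Protocol 9.2). Assumed: full recovery F of 90% or 95% in five participants, and partial recovery P of 80% down to 20% in one.

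Mean = (5F + P)/6; fall = F − mean = (F − P)/6.

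| P | F = 90%: mean (fall) | F = 95%: mean (fall) |
|---|---|---|
| 80% | 530/6 = 88.3 (1.7) | 555/6 = 92.5 (2.5) |
| 60% | 510/6 = 85.0 (5.0) | 535/6 = 89.2 (5.8) |
| 40% | 490/6 = 81.7 (8.3) | 515/6 = 85.8 (9.2) |
| 20% | 470/6 = 78.3 (11.7) | 495/6 = 82.5 (12.5) |

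Section 4.1.3 uses 90% as a discharge mark. With the other five at 95%, the mean falls below 90% once P is under 6 × 90 − 5 × 95 = 65%.

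**The case against.** **7.2 may be the operative rule.** It sits under the heading on leaving the study and can be read as saying how a 7.1 discontinuation is carried out. Elsewhere, leaving the study does not end all procedures: QTc cases have repeat ECGs, liver cases are monitored (Appendix 7), early withdrawals undergo the discharge assessments of that period if they agree (1.3), and release in Period 2 is to be agreed with the sponsor's study monitor (4.1.3). This has force. A reader might infer that the two instructions can never both be followed, or that collection will end; the documents do not go that far. But no text gives 7.2 precedence, 8.5.4 shows that the authors spelled out continued collection where they intended it, and the COVID-19 text in 1.3 is hard to square with remaining for excretion.

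**The SAP may not average the partial total.** A reader might infer that it would treat a truncated recovery as complete. It does not say so: the NS definition does not clearly fit a participant who has left, the cumulative value may simply be missing, and the OPS may settle the matter. Recovery is also listed by participant, so a short profile would be visible among six. This objection stands. What remains is silence on the handling of a primary endpoint.

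**A larger effect with four participants.** It is tempting to compute the fall for one truncated participant among four. That leaves three completers, and Protocol 4.1 and 9.2 provide for replacement when completers drop below four. With one replacement, P = 40% and F = 95%, the mean is (4 × 95 + 40)/5 = 84.0%, close to the 85.8% for six. No four-participant figure is used here.

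**Excluding truncated participants is selective.** In so small a sample, dropping someone because of a stopping event is not neutral, and a single exclusion rule tied to 4.1.3 could not be applied to Period 1. Both points stand, and the proposed change allows for them.

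**Conclusion.** The protocol is internally inconsistent on whether excreta collection continues after a stopping event. The COVID-19 text is the clearest conflict, and Period 1 has no recovery criterion under either instruction. It follows that collection for a primary endpoint may end early, not that it will. The SAP lacks a completeness criterion and a rule for intervals after departure, so a truncated total could enter mean cumulative recovery; the documents do not establish that it would.

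The illustrated fall of 1.7 to 12.5 points rests on three assumptions: exactly one of six truncated, recoveries in the ranges shown, and the partial total averaged with the rest. There is no effect if no stopping event occurs, if collection continues, or if the participant had already reached full recovery when he left. This should be corrected, but it does not invalidate the design.

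**What to change.** **Protocol.** The sponsor must reconcile 7.1.1, 7.1.2, 7.1.3, 7.1.5 and the COVID-19 text in 1.3 with 7.2 and 8.5.4, so that they agree on whether excreta collection continues after each kind of stopping event, in Period 1 as well as Period 2. Which clinical rule should apply is the sponsor's decision, and none is proposed here.

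**SAP.**
- Flag and list any participant whose collection ended before the planned 0–168 h intervals were complete (Period 1) or before the discharge assessment in 4.1.3 (Period 2). The flag depends on collection ending early, not on low recovery, so a participant with complete collection and low recovery is not flagged.
- Report mean cumulative recovery with and without flagged participants.
- State that intervals after departure are not coded NS and not set to zero.

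**Cost.** Wording in both documents and one extra summary. If an early stop occurs, the completers' mean rests on fewer participants, which is why both means are reported.
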